## **H.4 Survey and Interview Participants**

We will ask collaborators from each institution to identify individuals from each facility to participate in the surveys and interviews. We will ask the collaborators to engage organizational leaders at their facilities, including where possible a non-radiology health system leader, chief radiologist, radiologist, lead CT technologist, technologist, radiation safety expert, medical physicist and departmental administrator. Some of the participating facilities are very small (i.e. have only a single employee such as a radiology technologist), whereas others are large, and thus the number of available individuals varies. The individuals who participate in surveys will also ultimately help implement successful strategies (such as locking CT protocols).

## **I. Randomization**

The unit of randomization will be the facility cluster. Facilities will be randomly assigned to one of three tracks that determine the timing of when they receive the audits, in-person meeting, and multicomponent intervention. Randomization will be conducted using matching and re-randomization to ensure balance based on the following facility-level factors:

- 1) Total number of scans between December 1, 2015 and March 20, 2016. (measure of volume)
- 2) Total number of pediatric scans in the same time period.
- 3) Mean DLP of Abdomen, Chest, and Head scans in the same time period (to account for dose)
- 4) Proportion of Abdomen, Chest, and Head scans over benchmark (75th percentile of DLP) in the same time period.
- 5) Proportion of Abdominal Diameters that fall in the 1st-5th (quintile) size categories of overall population (to account for patient size)
- 6) Geographic location (Asia, Europe, West US, South US, Midwest US, Northeast US)
- 7) Time zone
- 8) A number of other facility characteristics based on self report including whether facility is:
  - A children's hospital
  - In the U.S.
  - Academic
  - A trauma center
  - Public / Private
  - Community hospital
  - Acute care facility
  - Tertiary referral hospital
  - Outpatient imaging facility

We will also apply these two additional conditions:

- 1) All facilities of the same "facility cluster" must be in the same track.
- 2) All facilities in a given track must be able to participate in phone calls at reasonable work hours, defined as 7 am – 5 pm local time. This means that some geographic locations cannot be in the same track.

A biostatistician not affiliated with UCSF, nor with other collaborators on this project, will perform the randomization.

## **J. Study Variables**

Data will be assembled via the UCSF-RDR for patient-level variables and CT examination-level variables and through surveys of each participating facility to assess facility - and institutional-level variables.

### **J.1 Patient-level Variables**

The patient-level variables of age and sex and anatomic area imaged will be extracted from the Radiology Information System (RIS) and PACS through the Radimetrics software and are available in the UCSF-RDR. A mid-scan diameter extracted from the CT image will be used as a surrogate for patient size and weight.

### **J.2 Examination/encounter-level Variables**

The specific protocol used for every imaging examination is recorded within the RIS and PACS and will be imported to the central server by Radimetrics. Anatomic area definitions will include head, neck, chest, abdomen/pelvis, combined chest/abdomen/pelvis (CAP), spine (cervical, thoracic, and lumbar), and extremity (although only some will be used in this study as described above). We will also develop and validate approaches for defining these anatomic areas using other collected variables, such as study description and protocol name. Setting (inpatient, outpatient, emergency department [ED]), time/day when examination was

conducted (time of day, day of week, and month), equipment (machine manufacturer, model and year), will be extracted from Radimetrics and used to assess as potential confounders.

### **J.3 CT Dose Metrics**

The radiation dose data will be assembled and stored for each radiation event. Radimetrics extracts direct measures of dose for each radiating event from the CT reports (CTDIvol and DLP) and calculates effective dose. Radiation dose indices will include effective dose, CTDIvol, and DLP. Our primary outcome measure will be effective dose. CTDIvol and DLP will be analyzed as secondary outcomes.

Assessing diagnostic accuracy is outside the scope of this project. However, we will ask radiologists on surveys about their satisfaction with image quality as part of the pre- and post-intervention interviews and surveys and will assess the association between satisfaction and dose.

### **J.4 Calculated Variables**

Dose indices will be assessed and presented graphically and in tabular format. They will be calculated prior to and following the simple audit report and the multicomponent intervention. The dose indices will be stratified by age (child, adult), anatomic area (head, chest, abdomen/pelvis, combined chest/abdomen/pelvis), and machine manufacturer and model, as well as geographically, e.g. by U.S. and non-U.S. location. Diagnostic reference levels (DRLs) will be created overall at baseline across all facilities using the interquartile range (IQR) and 75th percentile. The proportion of examinations above benchmarks will be calculated against fixed thresholds created during a single baseline period.

## **K. Study Endpoints and Planned Analyses**

### Endpoints:

The primary outcome is effective dose.

The Secondary outcomes include two other dose metrics, CTDIvol and DLP.

During each time period and within each anatomic area, we will assess the mean dose and the proportion of examinations above the baseline 75th percentile benchmarks (see above), for each facility. We will only assess doses in children if a facility has at least 12 examinations for at least one machine within at least one anatomic area during the audit period.

#### Planned analyses:

##### Primary Analysis

###### 1. Effective dose.

Time frame (see Section M for details):

Baseline 1: 9-12 months prior to simple audit;

Follow-up 1: 3-6 months following 4 weeks washout after simple audit;

Baseline 2: 2-6 months prior to multicomponent intervention;

Follow-up 2: 3-6 months following 2 weeks washout after multicomponent intervention;

Within each anatomic area, the mean effective dose and the proportion of CT scans with an effective dose over the benchmark during the Follow-up period will be compared to doses during the Baseline period. The benchmark for each anatomic area is defined as the 75th percentile of the dose distribution during Baseline 1.

##### Secondary Analysis

###### 1. Volumetric Computed Tomography Dose Index (CTDIvol).

Time frame and comparisons same as for Effective dose described above

###### 2. Dose Length Product (DLP).

Time frame and comparisons same as for Effective dose described above

### 3. Delayed effects: Effective dose, CTDIvol, DLP

Time frame (see Section M for details):

Baseline 1: 9-12 months prior to simple audit;

Follow-up 1: 3-6 months following 4 weeks washout after simple audit;

Baseline 2: 2-6 months prior to multicomponent intervention;

Follow-up 2 : 3-6 months following 2 weeks washout after multicomponent intervention;

Follow-up 3 : 12-15 months after multicomponent intervention

Within each anatomic area, the mean effective dose and the proportion of CT scans with an effective dose over the benchmark during Follow-up period 3 will be compared to doses during the Baseline periods prior to each intervention and the Follow up periods after each intervention.

### 4. Facilitators and Barriers associated with Effective dose and successful and failed implementation of dose optimization

We will use a linear mixed model analyses of changes in dose, and we will use mixed-methods approaches to identify facility-level factors (assessed through surveys of participating facilities) associated with effective dose levels and facilitators and barriers associated with successful and failed implementation of dose optimization (i.e., improvements of doses during Follow-up periods 1, 2, and 3 relative to Baseline periods 1 and 2).

## **L. Study Arms (Tracks)**

The study will divide facility clusters into three separate tracks. Each facility will first receive the simple audit, followed later by the multicomponent intervention, and will be staggered as to when they begin each intervention. Two of the three randomized tracks will be invited to participate in an in-person meeting, which will be timed to coincide with the audit for one of

the tracks and to coincide with the multicomponent intervention for one of the tracks. The third track will serve as a control (i.e., no in-person meeting). This will permit assessing whether the in-person meeting enhances the impact of the audit and/or multicomponent intervention.

### **L.1 Audit**

Audits will be sent to each facility summarizing their own doses and comparing them to the other facilities in their randomized track. The audits will be stratified by anatomic area and age group (adult/child) using each of the identified dose metrics. Facilities will be provided dose metrics in comparison to other facilities in their facility cluster, the healthcare institution, and overall compared with other facilities in their track and in the entire study. The audits will summarize data from a time period prior to provision of the audits and multicomponent interventions.

Each audit report will compare the facility against other facilities within their institution and to the other facilities/institutions in the study. The comparison will be made based on mean as well as median radiation doses, and the proportion of examinations above the baseline 75th percentile of radiation dose. Results will be provided both unadjusted and adjusted for patient size (using mid scan diameter as a surrogate for patient size). The audit reports will include descriptive tables and figures showing protocol-specific measures of radiation dose, outcome metrics indicating how their radiation doses rank against other facilities, stratification of results by age and anatomic area and results by the machine make and model. The audits will also provide information on patients who received very high doses.

After facilities receive the initial audit report, there will be a four-week (“washout”) period where facilities will have time to make changes to their imaging processes. For example, facilities can hold staff meetings or make any changes that could lead to dose optimization prior to when we assess their doses the next time. Facility leads will be responsible for developing plans for using audit data for quality improvement with our targeted suggestions; for example, meeting with technologists to review protocols or modifying existing protocols for a particular

anatomical area. This phase will test whether complete, comparative data alone can effect changes in dose levels.

Audit reports will be sent to “facility lead champions” (as requested/noted by the site PI) and facilities will be encouraged to share the information broadly with other contributors to radiologic practices at their facility or institution.

## **L.2. Multicomponent Intervention**

The multicomponent intervention will, in addition to the audit reports, provide a more detailed, tailored, facility-specific feedback (more detailed audit report) that will match the information provided on the audits to workable interventions and actionable suggestions for lowering doses. For example, not only will high dose protocols be identified, but also facilities will be provided with guidance on technical parameters that they could alter to match the performance of the best performing facilities. Further, the multicomponent intervention will include an invitation to participate in quality improvement collaborative calls where facilities will meet via teleconference regularly (weekly over 8 weeks) to learn about quality improvement and share experiences and challenges with adopting the various practices that we are promoting. These regular meetings between a UCSF established Change Team and a hospital created Implementation Team will help guide the implementation of the key aspects of the intervention.

Facilities will receive recommendations targeted to performance, which will be sent to individuals, identified by the PI at each facility, but will ideally include facility leads, heads of radiology departments, and Implementation Team leaders. Recommendations will focus on specific, alterable, technical factors (e.g., scan length); specific protocols to use more or less frequently (e.g. multiphase protocols); protocol modifications based on cross-facility analyses, etc. Recommendations will be tailored to the facilities practices. The audit reports will be a starting point for discussions about strategies and techniques to improve CT dose levels.

### Change/Implementation Team meetings and Quality Improvement Collaboratives:

The University of California based Change Team includes physicists, lead technologists,

radiologists, an administrator with extensive experience in departmental change who will be the liaison to facilities, and a leader in implementation research who knows how to implement change. Our facility lead champions will assemble local Implementation Teams based on the facility structure (e.g., who makes decisions about protocols or monitors legal issues). Members of the Change Team will advise facility leads on the creation of the Implementation Team. Implementation Teams will use baseline audit results to convey the importance of CT quality improvements to a broad audience. Change Teams will work with Implementation Teams (within the context of the RCT) to standardize practice, for example by showing the impact of organizational changes, creating disincentives for deviation, and providing monthly call access to physicists, technologists, or radiologists who can guide improvements. We will also regularly consult with our partners (including chief physicians, radiologists, and technologists) to understand what does and does not work and why. Close engagement of health care delivery staff as full partners will help to overcome critical implementation barriers. Examples of barriers might include CT systems that are too old to generate doses comparable to newer machines; or facilities that have so many protocols for imaging a single area that technologists cannot use them all in an optimized way; or that radiologists insist on multiphase or multi-sequence CT protocols without appreciating that those protocols are no longer considered state-of-the-art or understanding their impact on patient dose. These challenges each require different solutions and engagement of different individuals. Some facilities may be more resistant to change than others. We anticipate that comparative performance data combined with group assessment of the most effective strategies will be the strongest tools for local champions to encourage change. Thus, we will work with facility lead champions to collect and present appropriate dose metric data that will encourage action by senior hospital leadership.

Many of the facilities do not have experience in conducting quality improvement activities. We have engaged the Institute for Clinical Systems Improvement (ICSI) to provide background education on quality improvement to help our facilities create appropriate expectations and change team members.

Facilities receiving the multicomponent intervention will meet via WebEx online conferencing

with other groups in their randomization cluster to share experiences (Quality Improvement calls) weekly. Change and Intervention Teams will participate in these calls. Each meeting will include physicists and radiologists who will answer technical questions and provide specific examples and strategies for effective dose management. Topics will include change strategies such as development and application of standardized procedures and protocols. Facilities will report concerns and barriers for group problem solving and guidance. Leaders in implementation sciences will provide concrete suggestions for changing practice. Shared data from the groups in the cluster will allow the best performers to describe how they achieved goals and give low performers concrete steps toward more effective action. Collaborative implementation is an ideal strategy for pooling experience. Educational materials will be offered and encouraged in these collaborative meetings. During each WebEx conference, we will keep track of the number of participants from each facility who attend, the number of questions that are asked by each facility or comments that are made, and the sharing of specific cases as a way to score the relative engagement of individuals from each facility in the quality improvement collaboratives.

As with the audit intervention, the facilities will be responsible for determining how to use the provided advice to improve performance.

## **M. Timeline and Timeline of Assessments**

The facilities will be divided into three tracks (i.e. randomization groups), each containing approximately 37 facility clusters. Most facility clusters include a single facility, while some clusters will include several facilities that are integrated in how they perform CT. Tracks will receive interventions in a sequentially staggered fashion, with their order determined randomly (see below).

### **M.1. Graph of timeline (also included with attachments)**

In order to assess whether improvements in dose occur at or persist over a longer time period; we will compare doses 12-15 months after completion of the multicomponent intervention with baseline doses and doses after the simple audit and the multicomponent interventions.

## **N. Statistical Analysis**

### **N.1 Quantitative Analyses**

For each trial phase, we will compare radiation doses from a baseline period before that intervention starts with doses in a post intervention period, separated by a “washout” period during which facilities should have adequate time to a) absorb the feedback and messages from the intervention, and b) implement changes in scanning practices if and how they so choose.

The pre-audit/intervention and post-audit/intervention periods will vary in length of time according to: a) which type of intervention (simple or multicomponent), and b) which track (randomization group) the facilities are in. Please see Section M for details.

The primary outcome measure will be effective dose. Secondary outcomes will be CTDIvol and DLP. For each anatomic area studied and each dose metric, we will compare the mean dose and the percentage of CT examinations with dose levels above the baseline 75th percentile benchmark threshold. Dose metrics may be transformed (e.g., by applying the natural logarithm) prior to modeling the mean dose if necessary to meet linear model assumptions.

We will model mean doses (possibly transformed) using hierarchical linear regression and will model the percentage of doses above the threshold using hierarchical logistic regression, controlling for underlying time trends and for facility-level and patient-level covariates that could influence dose (e.g., facility size, patient age or sex, etc.). We will include random effects for machine, facility, and facility cluster to account for correlation among scans performed on the same machine, within the same facility, and/or within the same cluster of facilities. We will evaluate the effect of audit vs. no feedback on CT dose by testing whether dose levels decrease in the follow-up period after the audit vs. during the baseline period prior to the audit. We will use a similar approach for the multicomponent intervention but will include all periods in the

model, comparing post intervention to both original (pre-simple audit/intervention) baseline and new (pre-multicomponent audit/intervention) baseline after completion of the final collaborative calls of the multicomponent audit/intervention. We will use a similar approach for assessing delayed and/or longer-term changes by analyzing doses 12-15 months following the multicomponent intervention in comparison to doses in the earlier periods.

We will also compare the multicomponent intervention and simple audit effects to determine which is more effective. We will also compare how participation in the in-person meeting impacts the effects of the simple audit and multicomponent intervention by including interactions with an effect of in-person meeting and the particular intervention. Each facility will act as its own control, and we will control for underlying time trends, which are estimable because of the stepped-wedge design.

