## **H. Study Population and Unit of Analysis**

CT doses will be measured at the examination (i.e., encounter) level. Because examinations from the same machine, facility, and institution are structurally nested (hence non-independent), we will use appropriate statistical techniques to account for this correlational structure.

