## **O. Sample Size**

Statistical power depends on between-class coefficient of variation (standard deviation between facilities divided by average prevalence per facility). Based on prior research, we expect these values to vary between 0.4 and 1.1, depending on anatomical region and response metric. With 84 unique clusters, reflecting 116 facilities, to be randomized and at least 27-28 scans per facility for each anatomical region and age group (adult/children), in each measurement period, we will have an 80% power to detect a change of 5 percentage points (from 25% to 20%) in percentage of examinations with doses above the benchmark after the intervention versus baseline, using a two-sided significance level of 5%. The exceptions to this are children's head scans, which only require 15 scans per facility in each measurement period to achieve the same power with 84 clusters. We expect each facility to contribute, on average, at least 60 scans per day. With each measurement period being at least 1 month it is very likely 80% power will be surpassed. The effect of multicomponent intervention is expected to be greater than the effect of auditing; thus, the same sample size would also be sufficient in detecting the significance of multicomponent intervention.

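### The N.1 outcome model has no term for a facility drifting or responding differently from the rest; if facilities do, its standard errors for the intervention effects are too small, increasingly so as scan volume rises.

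*Combined protocol and SAP*

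**What the plan says.** Section N.1 fits hierarchical linear models to mean dose and hierarchical logistic models to the proportion of examinations above the benchmark, with time trends and covariates as adjustments. On correlation it says: "We will include random effects for machine, facility, and facility cluster to account for correlation among scans performed on the same machine"; the sentence then extends this to the facility and the cluster. The contrast of interest is within facility: "Each facility will act as its own control, and we will control for underlying time trends". The effect of the in-person meeting enters as an interaction with each intervention. N.2 reuses the same modelling approach to relate survey measures to change in dose.

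The documents mention no facility-by-period effect, random intervention effect, robust variance or permutation test. Yet they expect unequal response. The account of the Change and Implementation Teams in L.2 says: "Some facilities may be more resistant to change than others". Section G suggests larger reductions where the quality-improvement culture is strong, and N.1 leaves it to each facility whether and how to change its practice.

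Section O describes variation between facilities only through a CV: "we expect these values to vary between 0.4 and 1.1, depending on anatomical region and response metric". From 84 clusters and 27-28 scans per facility, anatomic region, age group and period, it claims "80% power to detect a change of 5 percentage points (from 25% to 20%) in percentage of examinations with doses above the benchmark". It then expects an average of at least 60 scans per day per facility and concludes: "With each measurement period being at least 1 month it is very likely 80% power will be surpassed". No correlation between periods is given.

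**The concern.** Each intervention is delivered to whole facilities and judged by a change between periods. Effects for machine, facility and cluster that do not vary with time cancel out of that change. What remains in the model's error is scan-to-scan noise, which shrinks as scans accumulate. Real facility-specific movement, such as an edited protocol or a stronger or weaker response to feedback, does not shrink with more scans. A model without a term for it counts each extra scan as independent evidence about the change.

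At stake are the confidence intervals and tests for the audit and multicomponent effects, the meeting interactions, and the survey predictors of change in N.2. The predictors are affected because facility-level characteristics would be tested as if scans, rather than facilities, were the evidence. The error runs towards declaring an effect.

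**Working it through.** **Inputs from section O:** proportion above benchmark 25% falling to 20%; two-sided 5%; CV 0.4 to 1.1; 84 clusters; 27-28 scans per facility-period; 60 scans per day. Section D gives three tracks, so 28 clusters each if equal.

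**Assumptions:** the layout, because the timeline figure is not shown; the CAC (the share of between-facility variance that is constant across periods), taken as 0.80 to 0.99; each cluster treated as one unit; a linear approximation for the proportion. Scan counts *m* per area and period are 28 (the plan's figure), 450 (a quarter of one month: 60 × 30 / 4) and 1,800 (90 days, three areas: 60 × 90 / 3).

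**1. The plan's 80%.** Take fixed period effects and one constant cluster effect with variance τ² = (CV × 0.25)². Power = Φ(0.05/SE − 1.96), with SE from generalised least squares. With 3 tracks and 3 periods:
- CV 0.4, scan variance 0.25 × 0.75 = 0.1875: *m* = 27 gives SE 0.0177 and power 80.7%; *m* = 28 gives SE 0.0174 and 81.9%.
- Scan variance 0.225 × 0.775 = 0.174, *m* = 28: power is 80.6% at CV 0.7 and 79.2% at CV 1.1.

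The stated power is thus what a model with time-constant cluster effects delivers. Other layouts give other values (four periods, CV 0.4, *m* = 28, scan variance 0.1775: 88%), so this supports that reading without proving it.

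**2. SE understatement.** Let the facility-by-period variance be w² = (1 − CAC)τ² and the scan variance σ² = 0.1875 − τ². If w² is present but not modelled, true SE / model SE ≈ √(1 + *m*w²/σ²), and type I error = 2Φ(−1.96/ratio).

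For CV 0.4 and CAC 0.95: τ² = 0.01, w² = 0.0005 (SD 2.2 percentage points), σ² = 0.1775.
- *m* = 28: √1.079 = 1.04, type I error 6%
- *m* = 450: √2.268 = 1.51, type I error 19%
- *m* = 1,800: √6.070 = 2.46, type I error 43%

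The sandwich variance for 3 tracks and 4 periods gives, for CAC 0.99 to 0.80:

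| Scans per facility-period | CV 0.4 | CV 1.1 |
|---|---|---|
| 28 | 1.01 to 1.13 | 1.09 to 2.2 |
| 450 | 1.1 to 2.5 | 2.0 to 7.9 |
| 1,800 | 1.4 to 4.6 | 3.6 to 15.6 |

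Simulated type I error at CV 0.4 agrees: 5.3% (*m* = 28, CAC 0.95), 17% (450, 0.95), 31% (450, 0.90) and 56% (1,800, 0.90).

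**3. Unequal response alone.** With no drift, an unmodelled intervention effect varying between facilities with SD 1 to 5 percentage points (assumed) gives ratios at *m* = 1,800 of 1.1 to 2.9 (CV 0.4) and 1.2 to 3.5 (CV 1.1).

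**4. Power for 5 points with the facility-by-period term modelled** (four periods, *m* = 1,800):
- CV 0.4: above 99% at every CAC tried
- CV 0.7, CAC 0.80: 88%
- CV 1.1: 97% (CAC 0.95), 80% (0.90), 51% (0.80)

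At CV 1.1 the last three barely move as *m* grows without limit, because w² then dominates.

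**The case against.** The strongest reply is that N.1 is brief rather than wrong. It never says that the random effects are intercepts and does not exclude further terms, and section H promises suitable methods for the nesting. That stands as a point about wording. But the listed effects are all the plan commits to, and an analyst following them would fit none that varies by period.

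Several stronger readings are tempting, and the documents do not support them:

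- *Standard errors several times too small, as a fact.* This needs an assumed CAC and hundreds to thousands of scans per facility-period. At 28 scans and CV 0.4 the error is negligible. A facility may enter with 120 scans in three months, about 40 a month over all areas. The 60 per day is an expected average, not clearly limited to eligible scans.
- *Dose treated as constant over time.* Common time trends, intervention effects and meeting interactions are in the model, and patient covariates take up some case-mix change. Only each facility's deviation from the common pattern is fixed.
- *Drift will be reported as an intervention effect.* With randomised timing, independent drift inflates variance and does not bias the estimate. False positives become more likely, not certain.
- *The trial is underpowered.* Among the cases computed at 1,800 scans, power falls to about 80% or below only at CV 1.1 with CAC 0.90 or lower.
- *Omitting institution, or a small-sample correction, explains the error.* Section H does name institution as a level ("Because examinations from the same machine, facility, and institution are structurally nested (hence non-independent"), but a time-constant institution effect largely cancels within facility. With 84 clusters, a small-sample correction moves the critical value only from 1.96 to about 1.99.

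**Conclusion.** The concern holds as a defect of the specified model. N.1 has no facility-by-period or facility-specific intervention term and no alternative inference that would cover for one, while the protocol itself expects response to vary. The direction is certain if such variation exists: standard errors are too small, and more so with more scans.

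The size is not fixed by the documents. For CAC 0.80 to 0.99 it runs from negligible at 28 scans and CV 0.4 to severe at the volumes section O anticipates, and it is larger at CV 1.1. These figures are for the above-benchmark proportion under an assumed layout. No SD or intraclass correlation is given for mean effective dose, so the size there is unknown, although the same formula applies. The section O statement that volume will carry power past 80% is safe at CV 0.4 but not over the whole stated CV range.

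**What to change.** In N.1, add a facility-by-period random effect (with a cluster-by-period effect for clusters of several facilities) and random facility-level effects for the audit and the multicomponent intervention. Apply the same structure to the meeting interactions and to the N.2 models of change. Alternatively, base inference on a cluster-robust variance or a permutation test at the 84 randomised clusters; a permutation test must follow the matching, re-randomisation and call-time restrictions in section I.

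In section O, state the assumed CAC, estimated from baseline registry data, and give power over a range of it. Qualify the sentence on scan volume: with the term modelled it holds at CV 0.4, but at CV 1.1 power is capped at about 80% for CAC 0.90 and about 51% for CAC 0.80, however many scans are added.

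The cost is SAP wording and somewhat longer model fitting. Confidence intervals will be wider and the power statement less favourable. No new data are needed.
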